All study children - 2017						
SMC	2000	200	10.0 (5.00, 15.0)	(Reference)		P=0.0
RTS,S	2000	200	10.0 (5.00, 15.0)	1.00 (0.90, 1.10)	Reference	
Combined	2000	200	10.0 (5.00, 15.0)	1.00 (0.90, 1.10)	1.00 (0.90, 1.10)	
Total	6000	600	10.0 (5.00, 15.0)	-	-	-
All study children - 2018						
SMC	2000	200	10.0 (5.00, 15.0)	(Reference)		P=0.0
RTS,S	2000	200	10.0 (5.00, 15.0)	1.00 (0.90, 1.10)	Reference	
Combined	2000	200	10.0 (5.00, 15.0)	1.00 (0.90, 1.10)	1.00 (0.90, 1.10)	
Total	6000	600	10.0 (5.00, 15.0)	-	-	-
All study children - 2019						
SMC	2000	200	10.0 (5.00, 15.0)	(Reference)		P=0.0
RTS,S	2000	200	10.0 (5.00, 15.0)	1.00 (0.90, 1.10)	Reference	
Combined	2000	200	10.0 (5.00, 15.0)	1.00 (0.90, 1.10)	1.00 (0.90, 1.10)	
Total	6000	600	10.0 (5.00, 15.0)	-	-	-

Numbers are included only to give an idea of layout / spacing.

Similar tables will be used to report the prevalence of other secondary outcomes measured at the end of transmission season surveys, and weekly surveys.

Figure 1. This will show i) cumulative hazards of malaria, by treatment group and ii) the risk of malaria, by treatment group.

References

5. RTS S Clinical Trials Partnership. First results of phase 3 trial of RTS,S/AS01 malaria vaccine in African children. *N Engl J Med.* 2011;365(20):1863-75.
6. RTS S Clinical Trials Partnership. A phase 3 trial of RTS,S/AS01 malaria vaccine in African infants. *N Engl J Med.* 2012;367(24):2284-95.
7. RTS S Clinical Trials Partnership. Efficacy and safety of RTS,S/AS01 malaria vaccine with or without a booster dose in infants and children in Africa: final results of a phase 3, individually randomised, controlled trial. *Lancet.* 2015;386(9988):31-45.
10. Zou G. A modified poisson regression approach to prospective studies with binary data. *Am J Epidemiol.* 2004;159(7):702-6.

Details of Amendments to the Statistical Analysis Plan

The Original SAP (dated 09-Apr-2020) was amended on one occasion (02-Jun-2020) and approved by the DSMB prior to locking and archiving of the trial database. In the amendment, two edits for clarification were made as detailed below.

Edit 1 - Clarification of passive case detection of the primary outcome (Page 6):

The text in bold italics was inserted as below.

Primary Endpoint

The primary end-point is the incidence of episodes of clinical malaria, as defined below, treated at a study health centre or hospital.

1.1 **Clinical malaria** is defined as an episode of fever (either measured temperature $\geq 37.5^{\circ}\text{C}$, or a history of fever within the past 48 hours), and a positive blood film, with a *P. falciparum* parasite density of 5,000 per μl or more. This cut-off has been used in previous studies of SMC in Burkina Faso and Mali, as well as in the phase 3 studies of the RTS,S/AS01 vaccine (1, 2, 5-7).

All passively-detected episodes of clinical malaria will be included in the analysis. ***Specifically, this includes visits to outpatient clinics and hospitals, as well as morbidity detected at the time of SMC or at the end of transmission season survey. These contacts can be considered 'passive' because the caregiver had to bring the child to the contact (and because the SMC or survey was conducted at the health facility in many cases). Morbidity detected at contacts for which study children were visited at home (for serological sampling, and for the weekly parasitaemia survey) are excluded, as is vaccination, because some children were visited at home and brought to the clinic to be vaccinated.***

To avoid double counting of disease episodes which result in more than one healthcare contact, episodes of the primary outcome documented within 7 days of a previous episode will not be counted. No adjustment is necessary to the person-time at risk (11).

Edit 2 – Clarification of the rationale for the definition of the ‘per protocol’ population

The text in italics was inserted as below:

Page 10:

As a secondary analysis, the primary outcome will also be analysed per protocol (PP). The PP population will be defined separately for each year of the study. Children who were **vaccinated** at all scheduled vaccination contacts in a particular year (3 in 2017, 1 in 2018, 1 in 2019) and who, in the same year, were also seen at the first SMC/SMC placebo contact each month (4 per year) will be considered as ‘per protocol’ for that year. Children who attended for **SMC** administration but who did not receive SMC because they had malaria and were referred for treatment will be included in the per protocol analysis.

‘Per protocol’ is defined differently for the two interventions (vaccination and SMC). For vaccination, a child must have received all vaccination doses that year; for SMC a child must only have attended all SMC contacts that year. This difference is necessary because the primary outcome of the trial (clinical malaria) can result in a specific SMC dose being missed permanently, whereas if a child had malaria at the time of vaccination, catch-up was attempted later in the season. The per protocol conditions will be applied equally to all three groups, i.e. to be considered as per protocol, a child must have received all doses of vaccine AND attended all SMC contacts, irrespective of which of these were active and placebo.

All secondary outcomes will be analysed by modified intention to treat as described above.

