2 STUDY OBJECTIVES

[figure not shown]
The trial seeks to determine whether –

- a. Seasonal vaccination following priming with the RTS,S/AS01 malaria vaccine would be non-inferior to SMC SP + AQ in preventing malaria in children in the areas of the Sahel and sub-Saharan Africa where malaria is still a major public health challenge and whether it would be easier to deliver.
- b. RTS,S/AS01 would provide additional, useful and cost effective protection against malaria if given together with SMC in areas with highly seasonal malaria transmission and reduce the risk of the emergence of resistance to the antimalarials used for SMC.

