Approximately 5 million children have received SMC with SP + AQ during the 2015 rainy season across the Sahel and sub-Saharan (http://www.malariaconsortium.org/pages/access-smc.htm) and this drug combination has been shown to be remarkably safe [10]. SP can cause Stevens-Johnson syndrome, but this side effect has been seen very rarely when SP has been used for either intermittent preventive treatment of malaria in pregnancy or SMC. Amodiaquine is bitter and may cause vomiting but serious side effects, which include liver damage and neurological side effects, are very rare. The possibility that SMC with SP+AQ might induce resistance to these drugs in *P. falciparum* has been investigated in a number of trials of SMC. Selection of parasites carrying mutations which confer resistance to pyrimethamine or sulphadoxine has been demonstrated in some but not all studies [7]. However, because the prevalence of parasitaemia in children who received SMC was substantially less than in the control group, the total number of parasites carrying resistance markers was less in children who had received SMC than in control children. Extensive use of SP for intermittent preventive treatment in pregnant women has not accelerated resistance to SP in West Africa. Preliminary analysis of samples obtained from children in an SMC trial in the study sites at the end of 2014 did not show levels of mutations in *dhfr* and *dhps* genes

likely to be associated with *in vivo* resistance to SP. The potential risk of inducing resistance to SP or AQ by SMC was reviewed carefully by a WHO Technical Expert Group and WHO's Malaria Policy Advisory Group and considered to be an acceptable risk in light of the major benefits conveyed by the intervention. Malaria parasites isolated at the end of the transmissions season will be tested for resistance markers to SP.

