10 FOLLOW-UP AND MEASUREMENT OF OUTCOMES

The following follow-up procedures required to measure the study outcomes are being undertaken

- a. ***Passive surveillance for cases of uncomplicated and severe malaria.*** In each country, project staff are based in the district hospital and in the main dispensaries that serve the study communities and, working with health service staff, they are responsible for identifying and documenting all cases of malaria who present to these health facilities. In Mali, cases of uncomplicated malaria may also be treated by community health workers who have been taught to diagnose malaria with a RDT and to treat RDT positive cases, and these cases are also being recorded if they meet the inclusion criteria. Cases of suspected malaria (fever, history of fever within 48 hours or any other symptom/sign suggestive of malaria) are tested with a RDT and managed on the basis of their RDT result and blood films

and filter paper strips are obtained from all these cases for subsequent confirmation of the diagnosis.

- b. **Active surveillance for malaria.** Each month throughout the study period, 96 randomly selected children (32 from each arm of the study) in each country will be visited at home, their temperature measured and a blood film collected for subsequent detection of asymptomatic parasitaemia. Any child who is febrile or who has other features suggestive of a diagnosis of malaria has an RDT done and those who are positive are treated with a full course of an ACT. This activity to cease for the final 3 months of the study, April – June 2020 due to the COVID-19 outbreak.
- c. **Prevalence of malaria parasitaemia and anaemia.** A survey of all study children is undertaken one month after the last round of SMC administration at the end each malaria transmission season. Temperature is measured and any child who is febrile or who has other features suggestive of a diagnosis of malaria has an RDT done; those who are positive are treated with a full course of an ACT. Finger prick blood samples are collected for preparing blood slides and blood spots on filter paper from all children. The prevalence of parasitaemia, including the presence of gametocytes, is detected by microscopy.

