14 STUDY OUTCOMES

Primary outcome: The primary outcome measure of the trial is the incidence of clinical malaria, defined as an episode of illness characterised by fever (temperature $\geq 37.5^{\circ}\text{C}$), or a history of fever within the past 48 hours, that is severe enough to require treatment at a health centre or by a community health worker and which is accompanied by a positive blood film with a parasite density of 5,000 per μl or more.

Secondary outcomes: Secondary outcomes include: -

- a. Blood slide or rapid diagnostic test (RDT) positive malaria defined as a clinical episode of an uncomplicated febrile illness (temperature $\geq 37.5^{\circ}\text{C}$), or a history of fever within the past 48 hours, with a positive blood film (any level of asexual parasitemia) or a positive RDT.
- b. Hospital admissions with malaria, including cases of severe malaria which meet WHO criteria for a diagnosis of severe malaria.
- c. The prevalence of malaria infection (symptomatic or asymptomatic parasitaemia) not severe enough to warrant a clinic visit detected in a subset of randomly selected children during home visits.
- d. The prevalence of malaria parasitaemia (including gametocytaemia), moderate and severe anaemia, and malnutrition at the end of the malaria transmission season.
- e. Serious adverse events (SAEs), including any deaths, occurring at any time during the study with special reference to any cases of meningitis, cerebral malaria or immune deficiency illness.
- f. Anti-CSP concentrations obtained after priming and after each booster dose, determined in a sub-sample of children.
- g. Comparison of the anti-CSP concentrations among children who received co-administration of SMC and RTS,S/AS01 versus those who received RTS,S/AS01 alone.

- h. The presence of molecular markers of resistance to SP and AQ in parasite positive samples collected at the final cross-sectional survey.
- i. The 28-day treatment response of subjects with asymptomatic *P. falciparum* malaria to treatment with SP+AQ.

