10. Zou G. A modified poisson regression approach to prospective studies with binary data. *Am J Epidemiol.* 2004;159(7):702-6.

RTS,S-SMC:**A comparative trial of
seasonal vaccination with the RTS,S/AS01 malaria vaccine,
seasonal malaria chemoprevention,
and of the two interventions combined****Revisions to the Statistical Analysis Plan:**

Revision Number	Date of Revision	Page Number(s)	Details
1	02-Jun-2020	6	Clarification of passive case detection of the primary outcome.
		10	Clarification of the rationale for the definition of the 'per protocol' population

Study title

A comparative trial of seasonal vaccination with the malaria vaccine RTS,S/AS01, seasonal malaria chemoprevention, and of the two interventions combined.

Clinical trial registration

Clinicaltrials.gov Identifier: [NCT03143218](https://clinicaltrials.gov/ct2/show/study/NCT03143218)

Study duration

April 2017 – March 2020

Study site

The trial is being conducted in Houndé district, Burkina Faso and in Bougouni district, Mali, sites of a previous trial ([NCT02211729](https://clinicaltrials.gov/ct2/show/study/NCT02211729)), which evaluated the effectiveness of adding azithromycin to the drug combination used for seasonal malaria chemoprevention.

Study objectives

This trial seeks to determine

1. Whether seasonal vaccination with RTS,S/AS01 is non-inferior to four monthly courses of seasonal malaria chemoprevention (SMC) with sulphadoxine-pyrimethamine plus amodiaquine (SP+AQ) in preventing clinical malaria and other adverse outcomes.
2. Whether the combination of these two interventions (i.e. seasonal vaccination with RTS,S/AS01 and SMC with SP+AQ) is superior to RTS,S/AS01 alone or SMC alone in preventing clinical malaria and other adverse outcomes.

These aspects are of equal priority.

Study groups

This is a double-blind, individually-randomised trial with three study arms.

The study groups, and abbreviated names used for ease of reference, are shown in the table below.

	Group		
	1) SMC 'SMC alone'	2) RTS,S/AS01 'RTS,S alone'	3) RTS,S/AS01+SMC 'Combined group'
April/May – June/July 2017	Rabies vaccine x 3	RTS,S/AS01 x 3	RTS,S/AS01 x 3
July/Aug – Oct/Nov 2017	SMC x 4	SMC placebo x 4	SMC x 4
June 2018	Hep A vaccine x 1	RTS,S/AS01 x 1	RTS,S/AS01 x 1

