2.4.1 The prevalence of asexual stage *P. falciparum* infection of any density

2.4.2 The prevalence of asexual stage *P. falciparum* infection with density ≥ 5000 per ul

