2.5 Other secondary outcomes

2.5.1 The prevalence of molecular markers of resistance to SP and AQ in children with *P. falciparum* infection, among samples collected at the final cross-sectional survey in December 2019. These include the dhfr 51-59-108 triple mutation, dhps-A437G, and dhps-K540E mutations for resistance to SP, and the pfcr1 K76T and pfmdr1 N86Y mutations for resistance to AQ.

2.5.2 The percentage of children with asymptomatic *P. falciparum* parasitaemia at the cross-sectional survey in December 2019, who, when treated with SP+AQ, have an adequate clinical and parasitological response (ACPR) after 28 days.

Serious Adverse Events

In addition to the comparison of incidence rates described above (section 2.2), serious adverse events (SAEs) defined as hospitalisations or death, occurring at any time during the study will be tabulated by study group according to their cause.

Safety signals from the RTS,S/AS01 phase 3 studies

The incidence of meningitis has been very low in the study cohort, with no events up to the 30th November 2019. A 95% confidence interval for the incidence rate of meningitis among children vaccinated with RTS,S/AS01 will be calculated.

The incidence of cerebral malaria among children vaccinated with RTS,S/AS01 will be investigated by comparing the RTS,S/AS01 groups with the SMC alone group, controlling for SMC status using an indicator variable. Cox regression will be used to obtain the hazard ratio and its 95% confidence interval.

The incidence of febrile convulsions not related to malaria or another obvious cause among children vaccinated with RTS,S/AS01 will be investigated as for cerebral malaria, i.e. by comparing the RTS,S groups with the SMC alone group, controlling for SMC status using an indicator variable. Cox regression will be used to obtain the hazard ratio and its 95% confidence interval. The subset of febrile convulsions that occurred within 7 days of vaccination will also be analysed.

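### The resistance-marker endpoint is confined to infected children, a group selected after randomisation, so a comparison of arms on it leaves out any reduction in the number of infections

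*Combined protocol and SAP*

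**What the plan says.** Protocol section 2, objective (b), asks among other things whether RTS,S/AS01 given together with SMC would "reduce the risk of the emergence of resistance to the antimalarials used for SMC". The SAP's Study objectives restate the second objective as whether the combination "is superior to RTS,S/AS01 alone or SMC alone in preventing clinical malaria and other adverse outcomes"; resistance is not named there.

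The marker endpoint is defined twice, each time with infected children as the denominator. Protocol section 14, outcome h, has "The presence of molecular markers of resistance to SP and AQ in parasite positive samples" from the final cross-sectional survey. SAP 2.5.1 has "The prevalence of molecular markers of resistance to SP and AQ in children with" P. falciparum infection at that survey, in December 2019.

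Infection at the same survey is an outcome in its own right: SAP 2.4.1 is "The prevalence of asexual stage *P. falciparum* infection of any density", shown by arm in planned Table 3. Under Analysis populations, the SAP applies modified intention to treat to every secondary outcome and makes no exception for 2.5.1. Neither document defines marker carriage over all surveyed children.

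Protocol section 7 gives the background on SMC and resistance. It reports that "Selection of parasites carrying mutations which confer resistance to pyrimethamine or sulphadoxine has been demonstrated in some but not all studies". It then says that, because parasitaemia was less common with SMC, "the total number of parasites carrying resistance markers was less in children who had received SMC than in control children".

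**The concern.** Which children enter the denominator of 2.5.1 depends on what the interventions did after randomisation. The infected children in one arm are not the randomised counterparts of those in another, so a ratio of marker shares between arms lacks the protection of randomisation despite the modified intention-to-treat label.

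The share also removes the route by which a vaccine would most plainly bear on objective (b). If RTS,S/AS01 lowers the number of infections in children who receive SMC, fewer children may carry resistant parasites even when the share among the remaining infections does not change. Read alone, 2.5.1 would then suggest that adding the vaccine makes no difference.

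The other resistance measures do not fill the gap. The 28-day response to SP+AQ (SAP 2.5.2) is also restricted to parasitaemic children, and the schoolchild survey (protocol section 10h) lies outside the randomised arms.

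**Working it through.** **Inputs from the documents**
- Expected parasite prevalence at the end-2019 survey: 7.5% of 3,000 children per site (protocol section 10g).
- Children who received a first vaccine dose: 2,777 + 3,143 = 5,920 (SAP, Sample size), or 5,920/3 = 1,973 per arm.
- Dropout: 5% per year, 15% overall (SAP, Sample size).

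**Assumptions, not in the documents**
- Infection 30% lower in the combined arm than with SMC alone. This borrows the SAP's planning effect for clinical malaria; 15% is the alternative.
- Infection of 7.5% in the SMC-alone arm. The protocol's figure is for trial children at a site, not for one arm.
- All marker shares.

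**The plan's own figure.** 0.075 × 3,000 = 225 per site, as the protocol states. No sample size, power or expected marker frequency is given for 2.5.1.

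**Number of infected children.** 5,920 × 0.85 = 5,032 and × 0.075 = 377. With compounded dropout, 5,920 × 0.95³ = 5,076 and × 0.075 = 381. So about 380 over three arms. Before dropout this is 1,973 × 0.075 = 148 in the SMC-alone arm, and 148 × 0.70 = 104 in the combined arm.

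**Relation between the two measures.** Carriage among all children = P(infected) × P(marker given infected). Hence carriage ratio = infection ratio × marker-share ratio, and 2.5.1 supplies only the last factor.

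| Contrast and assumed values | Infection ratio | Share ratio (2.5.1) | Carriage ratio |
|---|---|---|---|
| Combined / SMC alone, infection 30% lower, equal shares | 0.70 | 1.00 | 0.70 |
| Combined / SMC alone, infection 15% lower, equal shares | 0.85 | 1.00 | 0.85 |
| Combined / SMC alone, infection 30% lower, shares 50% v 40% | 0.70 | 1.25 | 0.875 |
| SMC / RTS,S alone, infection 6.25% v 10%, shares 35% v 25% | 0.625 | 1.40 | 0.875 |

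Row 1 with a share of 40% in both arms: 75 × 0.40 = 30.0 carriers per 1,000 with SMC alone, and 52.5 × 0.40 = 21.0 with the combination.

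For combined versus SMC alone, the two measures point in opposite directions only if the share ratio lies between 1 and 1/0.70 = 1.43, or between 1 and 1/0.85 = 1.18 for the smaller effect on infection.

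**Precision.** In row 1 with 40% shares and no dropout, expected carriers are 1,973 × 0.030 = 59 and 1,973 × 0.021 = 41. The standard error of the log ratio is √(1/59.2 + 1/41.4 − 2/1,973) = 0.20, so the 95% interval around 0.70 is about 0.47 to 1.04, and power is about 43%. With shares of 20%, power is about 24%. In row 3 it is about 11% for carriage and 35% for the share among infected children. If the share were 5% (assumed), 381 infections would give about 19 carriers over all three arms.

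**The case against.** **The share is a legitimate measure.** Marker frequency among infections describes selection in circulating parasites, and markers can be typed only where there are parasites. The documents never define what risk of emergence means, so preferring carriage is partly a choice of estimand. This stands, and it is the reason to keep 2.5.1. It does not make 2.5.1 a randomised comparison.

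**No contrast is named.** The SAP specifies no between-arm comparison for 2.5.1. One follows only by inference from the general model for survey outcomes. This stands too, but then nothing in the SAP answers the resistance part of objective (b).

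**Carriage can be derived.** The point estimate is the 2.4.1 prevalence times the 2.5.1 share, and with equal shares the 0.70 is simply the infection ratio. That is right. What is missing is a pre-specified ratio with its interval.

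**A stronger reading is not supported.** A reader might infer that 2.5.1 would point the wrong way on objective (b). SMC's selective clearance of sensitive parasites applies to both arms that receive SMC, and protocol section 7 compares SMC recipients with controls, not SMC plus vaccine with SMC. Nothing in the documents says that RTS,S/AS01 raises the marker share. The reversal in row 4 concerns SMC against RTS,S alone. On that row's figures, with the same infection and share in both SMC arms, combined versus SMC alone is 1.00 on both measures.

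**The assumed shares may be high.** The SAP describes marker prevalence in the previous trial in these districts as very low. This stands and limits what either denominator can show.

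**Conclusion.** The gap is real and moderate. The only marker endpoint in trial children conditions on infection, which the interventions affect, and it omits the effect of fewer infections. For the contrast in objective (b), the supported statement is that 2.5.1 can miss a benefit: 1.00 against 0.70 if infection is 30% lower and the shares are equal, or 1.00 against 0.85 if infection is 15% lower. Both reductions are assumptions.

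A change of direction for that contrast is arithmetically possible, but it rests on a difference in marker share for which the documents give no figure. For SMC against RTS,S alone, protocol section 7 itself describes how the share and the total can diverge, although the values in row 4 are illustrative.

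The conclusion depends on no numerical error in the plan. Because the SAP's restated second objective drops resistance, the two statements of the objective also need to be reconciled.

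**What to change.** Add to SAP 2.5.1, for each listed marker, the prevalence of marker-positive P. falciparum infection among all children surveyed in December 2019, by randomised arm. Count microscopy-negative children as not carrying the marker, and state how failed assays are handled. Report the prevalence ratio with a 95% CI from the Poisson model with robust standard error already specified for survey outcomes, giving combined versus SMC alone as the contrast for objective (b). Keep the share among infected children, labelled as a descriptive, non-randomised measure of selection. Either restore resistance to the SAP's second objective or explain its omission.

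The cost is a second denominator and a few sentences. Protocol section 10c provides that "A survey of all study children is undertaken one month after the last round of SMC administration", with slides and blood spots from every child, and section 10f plans marker testing of the microscopy-positive samples. The drawback is low precision, and very few carriers if markers remain rare, so the results should be presented as estimates with intervals.

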- d. **Serious Adverse Events.** Project staff based at the district hospitals are responsible for the identification of any child in the trial admitted to hospital and ensuring their referral to a study physician. Hospital staff have been provided with additional training on the recognition of cases of meningitis, cerebral malaria or immune deficiency diseases and standard operating procedures have been developed for management of children suspected of having one of these conditions. Definitions for meningitis and cerebral malaria, currently being developed by WHO for use in the pilot RTS,S/AS01 implementation trials are being used. The aetiology of cases of meningitis is determined by microscopical examination of cerebrospinal fluid samples for bacteria and white blood cells and by subsequent PCR testing at a reference laboratory. The death of any study child is investigated and, if this occurred in the community, a verbal autopsy is done.

Surveillance of all children will be maintained throughout the study period for any Serious Adverse Events (SAEs). Any SAEs that are (a) considered by the investigators to likely to be linked to the administration of a study vaccine or study drug or (b) are suspected cases of meningitis or cerebral malaria or (c) are fatal or life threatening are thoroughly investigated and reported to GSK and to the DSMB within 72 hours of their detection. All SAEs, whether

considered related to the study interventions or not are tabulated in a blinded fashion and provided to the DSMB and to GSK at the times requested by the DSMB. Details of definitions of adverse events and SAEs and of reporting procedures are described in appendix 1.

- e. *Immune response to the vaccine.*** Blood samples (2ml) have been collected from approximately 160 children in each of the groups (80 per country) who received RTS,S/AS01 prior to administration of the first dose of vaccine and one month after third dose of the primary series of vaccination, and then in year 2 and 3 before and one month after administration of the fourth and fifth doses of vaccine for measurement of anti-CSP antibodies.
- f. *Drug resistance:*** Dried blood spots from children who have malaria parasitaemia detected by microscopy at each annual cross-sectional survey will be used for analysis of molecular markers of resistance to SP and AQ at MRTC, Bamako.

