22 APPENDICES

Appendix 1: Definitions of adverse and serious adverse events and reporting schedule

a. Definition of an adverse event and serious adverse event

An adverse event (AE) is defined as any clinical symptom or sign that occurs in a study child after administration of the study vaccine or drugs that may or may not have a causal relationship with the study drugs. Examples of an AE include -

- (1) Occurrence of symptom such as fever, vomiting or diarrhoea in a child who did not have these symptoms prior to the administration of drugs;
- (2) Unexpected worsening of an existing condition.

A serious adverse event (SAE) is any clinical condition that fulfils at least one of the following criteria:

- a. results in death,
- b. results in admission to hospital,
- c. is life-threatening (the child was at risk of death at the time of the adverse event),
- d. results in disability/incapacity.

b. Severity, relationship of event to study drug or vaccine and outcome

The severity of a clinical adverse event is to be scored according to the following scale:

- (1) Mild: Awareness of sign or symptom, but easily tolerated.
- (2) Moderate: Discomfort enough to cause interference with usual activity.
- (3) Severe: Incapacitating with inability to work or perform usual activity.
- (4) Life-threatening: Patients at risk of death at the time of the event.
- (5) Death

c. Assessment of Causality

The relationship between the study vaccines and drugs and the occurrence of each SAE will be determined by the project physician in consultation with the site PIs based on their clinical judgment. Alternative causes, such as the natural history of the underlying diseases, concomitant therapy, other risk factors, and the temporal relationship of the event to the study drug will be considered and investigated. The site PIs will consult the lead PIs and the DSMB if this is deemed to be necessary.

There may be situations where the PIs have very minimal information about a SAE to include in the initial report. However, every attempt will be made to make an assessment of causality for every SAE prior for reporting to the IDMC. The PIs may change their opinion of causality in light of follow-up information, and may amend the SAE case report form accordingly.

The relationship of an adverse event to study vaccine or drug will be assessed according to the following definitions:

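### The SAP's by-group SAE table uses two of the protocol's four seriousness criteria, so a non-fatal life-threatening or disabling event without admission would fall outside it

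*Combined protocol and SAP*

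**What the plan says.** Appendix 1 of the final protocol states that an SAE "is any clinical condition that fulfils at least one of the following criteria". Four criteria follow. The first is death and the second is that the event "results in admission to hospital". The third begins "is life-threatening (the child was at risk of death at the time of the adverse event", and the fourth is that the event "results in disability/incapacity". The original protocol's Appendix 1 has the same four.

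Section 14 of the protocol makes SAEs secondary outcome (e): "Serious adverse events (SAEs), including any deaths, occurring at any time during the study". Section 10d adds two reporting routes. SAEs that "are fatal or life threatening are thoroughly investigated and reported to GSK and to the DSMB within 72 hours of their detection" form one named expedited category. Separately, all SAEs, whether "considered related to the study interventions or not are tabulated in a blinded fashion", go to the DSMB and the manufacturer.

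The SAP, under Serious Adverse Events, limits the tabulation by study group and cause to "serious adverse events (SAEs) defined as hospitalisations or death, occurring at any time during the study". The SAP of 09-Apr-2020 has the same wording. The June 2020 revision made two edits, on passive case detection and on the per protocol population, and did not touch this section.

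**The concern.** The two documents define the same term differently, and the narrower definition governs the comparative table. Followed as written, the SAP drops some events that the protocol counts under secondary outcome (e).

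Two things are at stake. First, an event serious enough for 72-hour reporting to the DSMB could be absent from the final by-group SAE table, and a reader could not reconcile that table with the listings compiled during the trial. Second, a reader of the final report could not tell whether there were no life-threatening or disabling events outside hospital, or whether such events were left out by definition.

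The protocol itself names reactions that could meet these criteria. It lists anaphylaxis (sections 7 and 9), Guillain-Barré syndrome for the rabies vaccine, and Stevens-Johnson syndrome and neurological effects for the SMC drugs (section 7). It describes those linked to the control vaccines and the SMC drugs as very rare. SMC is given at community points or at home (section 8), so an event could begin away from a hospital. The documents do not say whether any such event was managed without admission.

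**Working it through.** No figure in the plan bears on this point, so the check is a comparison of definitions.

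**Step 1: criteria side by side.**

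| Criterion | Protocol Appendix 1 | SAP SAE tabulation |
|---|---|---|
| Death | yes | yes |
| Hospital admission | yes | yes |
| Life-threatening | yes | no |
| Disability/incapacity | yes | no |
| Number of criteria | 4 | 2 |

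**Step 2: what falls in the gap.** Let D, H, L and I stand for events meeting the death, hospital admission, life-threatening and disability/incapacity criteria. Under the protocol, SAE = D or H or L or I. Under the SAP, SAE = D or H. The difference is (L or I) and not (D or H): a life-threatening or disabling event in a child who survived and was not admitted. Life-threatening or disabling events that led to admission or death are in both definitions.

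**Step 3: whether another SAP output fills the gap.**
- Section 2.2 (severe outcomes) covers admissions, blood transfusions in study hospitals and deaths. It has no outcome for life-threatening or disabling events as such.
- The section on safety signals from the phase 3 studies covers meningitis, cerebral malaria and febrile convulsions without malaria or another evident cause. None is stated to be limited to admitted children, so events of these three kinds may be counted there even without admission.
- The analysis of mortality in girls concerns deaths only.
- The planned main tables and the ancillary studies contain nothing further on SAEs.

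For life-threatening or disabling events of any other kind, without admission, no by-group output was found.

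**Step 4: whether both texts are current.** The four-criterion definition is in the final protocol and the two-criterion definition is in the revised SAP. The mismatch is not between superseded and current text.

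**Step 5: size.** Neither the protocol nor the SAP reports how many SAEs met only the life-threatening or disability criterion, or gives a rate from which this could be derived. The size cannot be computed.

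**The case against.** The strongest reply is that the gap has little practical effect. Section 10d rests SAE identification mainly on hospital staff who find admitted children, together with investigation of every death. General SAE surveillance is promised, but no method is described for finding life-threatening or disabling events elsewhere. Section 3 says severe malaria is managed at the district hospital, and most life-threatening events would be expected to end in admission or death. The SAP wording may simply describe what was systematically collected. That is a fair inference and it stands as a reason to expect few affected events. The SAP does not say so, however, and it does not remove the mismatch.

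It can also be said that those monitoring the trial lose nothing. That stands too: expedited reports, SAE forms and compiled listings follow the protocol definition whatever the SAP says.

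Two stronger readings are tempting, and the documents do not support them:
- A reader might infer that these events vanish from every safety analysis. They do not. Meningitis, cerebral malaria and febrile convulsions have their own analyses with no stated admission limit.
- A reader might try to size the gap from the febrile convulsion rate of about 1% that section 7 cites from the phase 3 trial. That would need the fraction of convulsions that were life-threatening or disabling without admission, and nothing in the documents bears on it. Section 7 adds that no lasting neurological effects were recorded, and the SAP analyses febrile convulsions separately.

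**Conclusion.** The point holds as a definitional inconsistency confined to the SAP's by-group SAE tabulation. The table uses two of four protocol criteria, no reason is given, and some protocol-defined SAEs would be excluded from a table that reports a protocol secondary outcome.

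It is a minor point. The number of events is not given and is probably small, possibly zero. That judgement assumes that most life-threatening events led to admission or death, which the hospital-centred ascertainment makes plausible but the documents do not show. The primary endpoint, the incidence comparisons of SAP section 2.2, the separate safety-signal analyses and safety oversight during the trial are unaffected.

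**What to change.** In the SAP's Serious Adverse Events section, replace the two-criterion definition by wording such as: *SAEs, as defined in protocol Appendix 1 (death, hospital admission, life-threatening, disability/incapacity), will be tabulated by study group and by cause.* Add one row giving, for each group, the number of SAEs that met only the life-threatening or disability criterion, with a note that ascertainment outside hospital may be incomplete. A stated zero in that row would be informative.

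If the restriction to admissions and deaths was deliberate, the alternative is to give the reason and still report that row.

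The cost is one phrase and one descriptive row. Appendix 1 already requires a report form for every SAE, so no new form is needed for events that were found; the documents do not show that all such events were found. The tabulation is descriptive, so the change affects no hypothesis test or error rate.
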